4.4.4 Sensitivity Analysis for Primary Endpoint

For the primary endpoint of the proportion of infants with B cell levels below the LLN, measured at Day 30 after the mother's first ocrelizumab post-partum infusion, a sensitivity analyses will be performed including those samples collected outside the assessment window as well as those taken while infant has an illness.

4.4.5 Supplementary Analysis for Primary Endpoint

No supplementary analyses are planned for the estimation of proportion of infants with B cell levels below the LLN.

For the estimation of ADID in the breastmilk, the following supplementary analyses may be performed:

 ADID will only be calculated in cases where the complete dose of ocrelizumab was administered. Any subjects experiencing ICE 1 (incomplete dosing) will therefore be excluded from this supplementary analysis.

4.4.6 Subgroup Analyses for Primary Endpoints

Subgroup analyses will be performed for the primary endpoint of the proportion of infants with B cell levels (CD19+ cells, absolute counts in blood) below the LLN, measured at Day 30 after the mother's first ocrelizumab post-partum infusion. Analysis will be presented for the following subgroups:

- The first dose of ocrelizumab post-partum (1x600mg, 2x300mg)
- Type of feed (breast milk, partial breast milk/infant formula)

4.5 SECONDARY ENDPOINTS ANALYSES

4.5.1 B Cell Levels in Infants

B cell levels (CD19+ cells, absolute counts and percentage of lymphocytes) in infants at Day 30 after the mother's first ocrelizumab post-partum infusion will be summarized descriptively in the FASI, irrespective of the occurrence of any ICEs identified for the primary endpoint.

4.5.2 Parameters to Evaluate the Transfer of Ocrelizumab into Breastmilk

The area under the milk concentration-time curve (AUC) of ocrelizumab in mature breastmilk (i.e., milk produced after Day 14 post-partum) over 60 days after the first post-partum ocrelizumab infusion will be calculated using the following time points depending on the dosing schedule:

- If receiving 1x600 mg: before infusion and at 24 hours (Day 1), 7 days, 30 days and 60 days post-infusion
- If receiving 2x300 mg: before infusion 1 and at 24 hours (Day 1), 7 days, 14 days, 15 days (24 hours after infusion 2), 21 days, 30 days and 60 days post-infusion 1

Summary statistics will be presented in the PASM for the following PK parameters of ocrelizumab in the breastmilk measured over 60 days after the mother's first postpartum ocrelizumab infusion, irrespective of the occurrence of any ICEs identified for the primary endpoint:

- Area under the milk concentration-time curve of ocrelizumab in mature breastmilk (AUC)
- Average ocrelizumab milk concentration (C_{mean})
- Peak ocrelizumab milk concentration (C_{max})
- Time to reach peak milk concentration (t_{max}, days)

Summary statistics for each parameter will be presented in the PASM, irrespective of the occurrence of any ICEs identified for the primary endpoint. A corresponding listing will be produced.

For summary stats of all PK parameters other than AUC, concentrations reported as BLQ are set to zero. For AUC calculation, BLQ values before the first measurable concentration are set to zero, and to missing after the last measurable concentration.

Other PK and exposure parameters may be calculated and summarized as appropriate, based on the data obtained.

Subject-level plots of the concentration of ocrelizumab in breastmilk over time will be produced in the PASM.

4.5.3 Relative Infant Dosage (RID) and Maximum Oral Daily Infant Dosage (MDID)

The estimated maximum oral daily infant dosage (MDID) will be calculated at the subject level as the peak ocrelizumab milk concentration measured over 60 days after the mother's first post-partum ocrelizumab infusion multiplied by an estimated infant milk intake of 150 mL/kg/day.

The average relative infant dose (RID, %) over 60 days will be calculated as the ADID (μ g) divided by the average maternal dosage (μ g) over 60 days multiplied by 100.

i.e.,

Average Oral Daily Infant Dosage (ADID) (A) = $9 \mu g$

Average maternal dosage over 60 days (B) = total dose / 60 = 600 mg / 60 = 10 mg = 10,000 μ g

Average RID (%) based on ADID = $(A / B) \times 100 = (9 / 10,000) \times 100 = 0.09\%$

The maximum RID (%) will also be calculated, where MDID is substituted for ADID in the formula above, i.e.

Maximum RID (%) = (MDID / Average maternal dosage over 60 days) x 100

Breastmilk ocrelizumab concentrations reported as BLQ will be imputed to zero for the calculation of summary statistics.

Summary statistics for MDID, average RID and maximum RID will be presented in the PASM, irrespective of the occurrence of any ICEs identified for the primary endpoint.

The analysis will be repeated for the following subgroups:

• The first dose of ocrelizumab post-partum (1x600mg, 2x300mg)

4.5.4 Infant Serum Concentration of Ocrelizumab

To evaluate whether there is transfer of ocrelizumab from the mother to the infant via breastmilk, serum concentrations of ocrelizumab in the infant are measured 30 days after the mother's first ocrelizumab post-partum infusion.

Ocrelizumab concentrations reported as BLQ will be imputed to zero for the calculation of summary statistics.

Summary statistics for the serum concentration of ocrelizumab in the infant will be presented in the PASI, and a corresponding listing produced.

4.5.5 Infant Absolute Antibody Immune Response

The infant's antibody (immunoglobulin [IgG]) immune response to common childhood immunizations with full or partial doses given prior to 1 year may include (but is not limited to) responses to MMR, diphtheria, tetanus, and pertussis (DTaP), Hemophilus influenzae type b (Hib), hepatitis B virus (HBV) and 13-valent pneumococcal conjugate vaccine (PCV-13), measured 1 month after the first or second dose of MMR vaccine or at Month 13 of age (+30 days) in case MMR vaccine is not planned to be administered.

Summary statistics for each serum IgG antibody titer will be presented in the AIRI, and a corresponding listing produced. Results for MMR titers and other vaccine induced antibodies will be summarized together irrespective of whether or not the infant received MMR vaccine. Listings will include whether or not the mother switched to another DMT regardless of timing.

4.5.6 Infant Positive Antibody Immune Response

The number and proportion of infants with positive humoral response (seroprotective titers as defined for the individual vaccine) will be presented for each IgG antibody titer in the AIRI population. Analysis will be presented by total as well as by women not switching to another DMT vs switching to another DMT regardless of timing.

A corresponding listing will be produced.

Seroprotective titers are defined for each vaccine in the table below:

Vaccine test	Seroprotective Titer
Bordetella pertussis antibodies, IgG	> 1.04 COI
Haemophilus influenzae B, IgG	≥ 0.15 µg/mL
Anti-Diphtheria IgG(-70)CL	≥ 0.01 IU/mL
Anti-Tetanus Toxoid IgG(-70)RUO	≥ 0.01 IU/mL
13 Valent anti-pneumococcal antibody panel	≥ 0.35 µg/mL
Anti-Measles Vir IgG(-70)CL	≥ 120 mIU/mL
Anti-MumpsAT Vir iGG(-70)CL	≥ 17 U/mL
Anti-Rub Vir IgG(-70)RUOCL	≥ 10 IU/mL
Anti-HBs	≥ 10 mIU/mL

COI=Cut-off Index; IU=International Unit IgG=immunoglobulin G.

Source: Storsaeter et al. 1998; EMA 2015.

For Tetanus and Diphtheria, a sensitivity analysis will be conducted using a seroprotective threshold of ≥ 0.1 International Unit (IU)/mL for infants receiving a 4th dose at least one month prior to the titer assessment. The ≥ 0.01 IU/mL threshold will still be used for those only receiving 3 doses.

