- Documentation of vaccinations: Infants will receive vaccinations according to the immunization schedule recommended in each participating country. The safety and timing of vaccination of the infant should still be discussed with the mother, in particular the vaccination with live-attenuated vaccines (e.g., MMR) for which the results on B-cell levels at 30 days after the first postpartum ocrelizumab infusion may be informative. Vaccines administered from birth throughout the end of the study should be recorded at Months 2, 4, 6, 9, and 12 as well as at Month 13/1 month after first or second MMR dose, and may include diphtheria, tetanus, and pertussis, Hemophilus influenzae type b (Hib), 13-pneumococcal conjugate vaccine (PCV-13), HBV and MMR. Documentation of vaccinations will be collected by the investigator via interview and documentation provided by the mother (e.g., vaccine card) or via direct contact with the pediatrician.

See Appendix 1 (Schedule of Assessments) for the timing of assessments and Appendix 6 for the time windows for infant growth velocity and child developmental milestone assessments.

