# Month 13 of chronological age (+30 days) if MMR is not planned to be administered

Mean titers (IgG) of antibody immune response(s) to common childhood vaccinations with full or partial doses given prior to 1 year will be measured (which include responses to MMR, diphtheria, tetanus, pertussis, Hib, HBV, and PCV-13). Titers will be measured at 1 month (+30 days) after the first or second dose of MMR vaccine, or at Month 13 of age (+30 days) if MMR vaccine is not planned to be administered.

Note: While vaccination schedules are not exactly the same from country to country, all participating countries are expected to provide the specific vaccines for the planned titer assessments.

a) **Lymphocyte subtypes:** A blood sample will be collected to measure B-cell counts (CD19+); the same sample will be used to measure T-cell counts (CD3+, CD4+, CD8+), and NK cell counts (CD16+CD56+).

Note: If the infant's B-cell levels are found to be below LLN at any visit, analyses of B-, T-, and NK cells will be repeated every 4 weeks until B-cell levels are found to be above the age-adequate LLN as per Appendix 7 (in consultation with the Sponsor). The first repeat analysis will also include a CBC and immunoglobulin levels.

Infant samples will be collected by venipuncture *at one timepoint*. As per the recommendations of the European Commission ad hoc group (2008), the total blood volume to be collected from an infant in a clinical study should not exceed 0.8–0.9 mL/kg at any time point, or 2.4 mL/kg over any 4-week period throughout the study. If the blood volume collected for an infant (as a result of these limits) is insufficient to carry out all planned assessments, Table 4 shows the order of priority for assessments.

Table 4 Prioritization Order for Infant Blood Sample Assessments
1 Month (+30 days) After the First/Second Dose of MMR Vaccine
or at Month 13 of Age (+30 Days) if MMR Vaccine Is Not Planned
to Be Administered

Order of Priority	Assessment
1	Any necessary safety laboratory samples (scheduled or unscheduled and performed at the discretion of the investigator)
2	Mean titers (IgG) of antibody immune response(s) to vaccinations a
3	Lymphocyte subtypes blood sample b

Ab = antibody; IgG = immunoglobulin G; MMR = measles, mumps, rubella; NK = natural killer; PCV = 13-valent pneumococcal conjugate vaccine.

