- a The following antibody titers will be measured: anti-measles Ab IgG, anti-rubella Ab IgG, anti-mumps Ab IgG, PCV-13 Ab (all serotypes), anti-tetanus toxoid IgG, anti-diphtheria IgG, Bordetella pertussis Ab IgG, hepatitis B surface Ab, and Hemophilus influenzae B IgG.
- b The same sample will be used to measure B-cell counts (CD19+), T-cell counts (CD3+, CD4+, CD8+), and NK cell counts (CD16+CD56+).

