4.1.10 Safety Analysis Set (Infants)

The safety analysis set of infants (SAFI) will be the same as the FASI.

4.1.11 Antibody Immune Response Analysis Set (Infants)

The antibody immune response analysis set of infants (AIRI) will include all infants in the SAFI for whom any serum titers of antibody immune response to vaccinations are available. This analysis set will be used to analyze humoral immune responses to common childhood immunizations.

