- As per the recommendation of the EC ad hoc group (2008) the total blood volume to be collected from an infant in a clinical study should not exceed 0.8–0.9 mL/kg at any timepoint, or 2.4 mL/kg over any 4-week period throughout the study. If the blood volume collected for an infant (as a result of these limits) is insufficient to carry out all planned assessments, the order of priority for assessments is as follows: for sample at Day 30 (±2 days) post-infusion 1, (1) safety laboratory samples [scheduled or unscheduled and performed at the discretion of the investigator] (2) lymphocyte subtypes sample for B-cell counts (CD19+) and T-cell counts (CD3+, CD4+, and CD8+), and NK cell counts (CD16+CD56+). (3) serum ocrelizumab concentration; for the Month 13 of age/1 month after first/second MMR vaccine dose sample, (1) safety laboratory samples [scheduled or unscheduled and performed at the discretion of the investigator] (2) serum titers of antibody response to immunizations (3) lymphocyte subtypes sample for B-cell counts (CD19+) and T-cell counts (CD3+, CD4+, and CD8+), and NK cell counts (CD16+CD56+).
- ^z For 1 month (+30 days) after the first or second dose of MMR vaccine, or at Month 13 of age (+30 days) if MMR vaccine is not planned to be administered, all efforts will be made to collect samples. However, if they cannot be collected, it will not be considered a protocol deviation.
- aa Serum anti-vaccine antibody (IgG) titers will be measured to vaccines administered as per local practice over the first year of life (which include MMR, *diphtheria, tetanus, pertussis*, Hib, HBV and PCV-13); 1 month (+30 days) after the first dose of MMR vaccine (if first dose is administered at 11 months of age or later) or 1 month (+30 days) after second dose of MMR vaccine (if first dose is administered before 11 months of age), or at Month 13 of chronological age (+30 days) if MMR vaccine is not planned to be administered.

- bb Vaccines administered from birth throughout the end of the study should be recorded at Months 2, 4, 6, 9, and 12 as well as at Month 13/1 month after first or second MMR dose.

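### MMR titers are to be summarized whether or not the infant had MMR vaccine, so the measles, mumps and rubella results may mix vaccine response with vaccine uptake

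*SAP*

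**What the plan says.** SAP 4.5.5 (Infant Absolute Antibody Immune Response) sets the rule for the titer summaries: "Results for MMR titers and other vaccine induced antibodies will be summarized together irrespective of whether or not the infant received MMR vaccine". SAP 4.5.6 (Infant Positive Antibody Immune Response) says that the number and proportion of seroprotected infants "will be presented for each IgG antibody titer in the AIRI population". SAP 4.1.11 defines that set as "all infants in the SAFI for whom any serum titers of antibody immune response to vaccinations are available", with no condition on vaccine receipt. The only split planned in 4.5.6 is by whether the mother switched DMT.

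Infants without MMR are part of the design: if MMR is not planned, the blood sample is taken at Month 13 of age instead of one month after an MMR dose.

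Two places describe which titers are assayed:

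- Footnote aa of the schedule of assessments (Protocol Appendix 1, repeated in SAP Appendix 2): "Serum anti-vaccine antibody (IgG) titers will be measured to vaccines administered as per local practice over the first year of life".
- Protocol 4.5.3.3, Table 4 footnote a: "The following antibody titers will be measured: anti-measles Ab IgG, anti-rubella Ab IgG, anti-mumps Ab IgG", followed by the other antigens, with no condition on receipt.

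The secondary objective in the protocol synopsis is whether infants can mount humoral responses to clinically relevant vaccines.

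**The concern.** One table across the two sampling visits makes sense for tetanus, diphtheria, pertussis, Hib, hepatitis B and pneumococcus, because infants on either path may have had those vaccines. The SAP sentence goes further and names MMR titers without an exception.

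An infant who never had MMR carries no information about response to it. If that infant's measles, mumps and rubella IgG are measured and tabulated, a value below the cut-off is counted as failure to respond and a value at or above it as a vaccine response. Neither is correct, and the summary table gives no sign of it.

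Receipt may also depend on the effect under study. Protocol 4.5.3.2 says the timing and safety of live vaccines such as MMR should be discussed with the mother, "for which the results on B-cell levels at 30 days after the first postpartum ocrelizumab infusion may be informative". A low B-cell count could therefore lead to no MMR, and the missing vaccination could then appear in the table as a failed immune response. With about 10 infants, one or two such cases would change how the result reads.

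**Working it through.** **1. The plan's own precision figures.** The response proportions use two-sided 95% Clopper-Pearson intervals (Protocol 6.5.2). For x of n, the lower limit is the 0.025 quantile of Beta(x, n−x+1) and the upper limit the 0.975 quantile of Beta(x+1, n−x). The documents give precision only for the B-cell endpoint (SAP 2.2, n = 10), which serves to check the method:

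- 1/10: 0.0025 to 0.4450, width 0.4425 (stated 0.443)
- 2/10: 0.0252 to 0.5561, width 0.5309 (stated 0.531)
- 0/10: upper limit 0.3085 (stated below 0.31)

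All three reproduce.

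**2. Inputs for the MMR rows.** N = 10 is the minimum enrolment. The documents do not give the number of MMR non-recipients, k, so it is assumed to range from 0 to 3. It is also assumed that every recipient is seroprotected and that every non-recipient is assayed and seronegative.

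**3. Seroprotection.** Pooled rate = (10−k)/10; recipients-only rate = (10−k)/(10−k). When x = n, the lower limit is 0.025^(1/n); for 8/8 this is 0.025^(1/8) = 0.631.

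| k | Pooled (95% CI) | Recipients only (95% CI) | Difference |
|---|---|---|---|
| 0 | 10/10 = 100% (69.2–100) | 10/10 = 100% (69.2–100) | 0 points |
| 1 | 9/10 = 90% (55.5–99.7) | 9/9 = 100% (66.4–100) | 10 points |
| 2 | 8/10 = 80% (44.4–97.5) | 8/8 = 100% (63.1–100) | 20 points |
| 3 | 7/10 = 70% (34.8–93.3) | 7/7 = 100% (59.0–100) | 30 points |

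A pooled 7/10 could come from 7 of 7 recipients responding (59.0–100%) or 7 of 10 (34.8–93.3%). The planned table cannot separate the two.

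**4. Mean titer.** Pooled mean = [(10−k) × recipients' mean + k × non-recipients' mean]/10. With non-recipient titers near zero this is (10−k)/10 of the recipients' mean, so 0, 10, 20 or 30% lower for k = 0, 1, 2 or 3.

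**5. The reverse bias.** Suppose k infants with low Day 30 B cells are not vaccinated and would not have responded. The recipients-only rate is then 100%, whereas vaccinating all 10 would have shown 100, 90, 80 or 70%. For k = 2 that is 8/8 (63.1–100%) against 8/10 (44.4–97.5%).

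**6. Which infants are assayed.** Under footnote aa, an infant without MMR has no MMR titers, k is effectively zero and nothing is distorted. Under a literal reading of the Table 4 panel, that infant is assayed and enters both summaries. Neither document says which governs.

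**The case against.** The strongest reply is that the sentence only merges the two sampling visits. SAP 4.5.5 describes the endpoint as response to immunizations given, in full or in part, before one year, and its own wording treats MMR titers as vaccine-induced. The Table 4 footnote can be read as a list of assays and footnote aa as their scope, in which case the two agree and the effect is zero. That reading is possible, but it has to be inferred against a sentence that expressly sets MMR receipt aside.

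Protocol 6.5.2 asks for response proportions in the overall population, which the AIRI denominator follows. That does not settle who belongs in an MMR denominator.

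Restricting to recipients conditions on something decided after exposure and possibly influenced by the B-cell result. This stands: step 5 shows a bias of the same size in the other direction. It is why a recipients-only figure should not appear without the non-recipients beside it.

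The any-titer entry rule applies to other vaccines as well. However, MMR is the only one for which the design provides a separate path for infants who do not receive it.

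The size rests on an assumed k, and the protocol says that "all participating countries are expected to provide the specific vaccines for the planned titer assessments". This also stands. Availability does not guarantee receipt by each infant, but the range must start at zero.

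Finally, titers and infant vaccinations are both listed (SAP 4.5.5, 4.5.6 and 4.3.2), so a reader could rebuild the figure case by case. That limits the harm without correcting the planned summary.

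**Conclusion.** The concern holds in conditional form. As written, the SAP includes MMR non-recipients in the measles, mumps and rubella titer summaries and, through the AIRI denominator, in the seroprotection proportions, if they are assayed. The documents do not settle whether they are.

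With full MMR uptake, or if non-recipients are not assayed, the effect is zero. Otherwise, with 10 infants, all recipients responding and non-recipients seronegative, each non-recipient takes 10 percentage points off the pooled proportion and about 10% off the mean titer. Seropositive non-recipients would dilute the proportion less, but would still not represent a vaccine response.

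The endpoint is secondary and descriptive, and no test or error rate is affected. The change should be made because it is cheap and keeps non-vaccination from being reported as non-response.

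**What to change.** - Limit the pooling of post-MMR and Month 13 results in SAP 4.5.5 to the non-MMR antigens.
- For measles, mumps and rubella, base the titer summary and the seroprotection proportion on AIRI infants with a measured titer and at least one documented MMR dose before the blood draw.
- Add a separate row for non-recipients giving their number, any measured MMR titers and their Day 30 B-cell status, or state that MMR titers are not assayed in them.
- Reconcile footnote aa of the schedule of assessments with Table 4 footnote a in Protocol 4.5.3.3.

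The cost is SAP wording and one table row. Day 30 B cells are already measured, and the vaccination record is already required: "Vaccines administered from birth throughout the end of the study should be recorded at Months 2, 4, 6, 9, and 12", and again at the final infant visit (Protocol 4.5.3.2). SAP 4.5.6 already uses dose history in its tetanus and diphtheria sensitivity analysis, so conditioning on receipt fits its approach. The drawbacks are a smaller denominator with a wider interval, and a recipients-only rate that may leave out infants with low B cells. The recipient and non-recipient rows must therefore be read together.

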ADID = average oral daily infant dosage; ASQ-3 = Ages and Stages Questionnaire, version 3; AUC = area under the milk concentration-time curve; CIS = clinically isolated syndrome; EDSS = Expanded Disability Status Scale; HBV = hepatitis B virus; Hib = Hemophilus influenzae type b; LLN = lower limit of normal; LMP = last menstrual period; MDID = maximum oral daily infant dosage; MMR = measles, mumps, and rubella MS = multiple sclerosis; PCV-13 = 13-pneumococcal conjugate vaccine; RID = relative infant dose; WHO = World Health Organization.

Table 1 Objectives and Corresponding Endpoints (cont.)

Objectives	Corresponding Endpoints	
Secondary Outcome Measures (cont.  • To evaluate the relative and maximum exposure to ocrelizumab in infants of lactating women with CIS or MS receiving ocrelizumab postpartum		
	Note: Other pharmacokinetic and exposure parameters may be calculated as appropriate, based on the data obtained.	
To evaluate whether there is transfer of ocrelizumab from the mother to the infant via breastmilk	Serum concentration of ocrelizumab in the infant measured at Day 30 after the mother's first ocrelizumab postpartum infusion	
To evaluate whether infants of lactating women with CIS or MS receiving ocrelizumab postpartum are able to mount humoral immune responses to clinically relevant vaccines	
 
Mean titers of antibody immune response(s) to common childhood vaccinations with full or partial doses given prior to 1 year, which include responses to MMR, diphtheria, tetanus, pertussis, Hib, HBV, and PCV-13
 
Proportion of infants with positive humoral response (seroprotective titers; as defined for the individual vaccine) to vaccines
 
	
Safety Objectives		
To evaluate the safety of ocrelizumab in lactating women with CIS or MS receiving ocrelizumab postpartum and in their respective infants	Rate and nature of adverse events in the mother throughout the study, including changes in clinical and laboratory results	
	
 
Rate and nature of adverse events in the infant throughout the study, including infections and hospitalizations
 
	

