### 4.1.1 Inclusion Criteria

The following criteria must be met for study entry:

- An Informed Consent Form (ICF) for participation of the maternal subject and her infant (for collection of blood, infant demographic and adverse event data) is signed and dated by the subject. Where applicable, the written ICF with respect to the infant is also signed and dated by the holder of parental rights as designated by the maternal subject
- Woman is able and willing to comply with the study protocol, according to the judgment of the investigator, in particular:
  - Woman is willing to breastfeed (either exclusively, or with formula supplementation) for at least 60 days after the first postpartum ocrelizumab infusion (this decision is to be taken prior to and independent from study participation)
  - Woman is willing to provide breastmilk samples before and after their first and, if applicable, second postpartum ocrelizumab infusion
    - Note: Exposure to ocrelizumab includes administration of an initial split dose of two 300 mg infusions (in 250 mL 0.9% sodium chloride) separated by 14 days for women initiating treatment with ocrelizumab, or a single 600 mg infusion (in 500 mL 0.9% sodium chloride) for women already on treatment with ocrelizumab.
- Woman is between 18 and 40 years of age at screening
- Woman has a diagnosis of MS or CIS (in line with the locally approved indications)

- Woman has delivered a healthy term singleton infant (≥37 weeks gestation)
- Infant is between 2–24 weeks of age at the time of the mother's first postpartum dose of ocrelizumab
- For women who received commercial ocrelizumab (OCREVUS) before enrolment: documentation that last exposure ocrelizumab occurred more than 3 months before the LMP (i.e., excluded a potential fetal exposure) and was given at the approved dose of 2×300 mg or 1×600 mg
- Woman agrees to use acceptable contraceptive methods or alternative methods during the study as described below and, if applicable, upon study treatment discontinuation, as defined by the local prescribing information (see Section 4.6.1).

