Study description: In this prospective, multicenter, open-label study, lactating women with CIS or MS (in line with the locally approved indications) who decided together with their treating physician to continue on, or start treatment with, commercial ocrelizumab post-partum will enter a screening period, which may be started during the third trimester of pregnancy and continue until 24 weeks post-partum. Women who have delivered a healthy term infant and made a decision to breastfeed their infant will be enrolled if they and their infants fulfil the respective eligibility criteria. Women resuming treatment with ocrelizumab post-partum will be included only if the last exposure to ocrelizumab occurred more than 3 months before the LMP (i.e., women without potential fetal exposure). In the 60-day (±2 days) treatment and sampling period, women will receive the ocrelizumab dose regimen as per the locally-approved label, at any point between Week 2 and Week 24 post-partum. The first dose of ocrelizumab may be administered as two 300-mg infusions separated by 14 days (for those initiating ocrelizumab) or as a single 600-mg infusion (for those resuming ocrelizumab). For women where a decision not to administer a second 300 mg infusion is taken after enrolment, continuation in the study will be allowed. Women referred by healthcare professionals to participate in the trial may receive ocrelizumab treatment at their neurologist's site as part of their standard of care treatment. Laboratory and clinical assessments will be performed at the designated visits.

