4.3.2 Infants

The following baseline characteristics of infants will be summarized and listed in the FASI, unless otherwise stated:

Characteristics at Birth

- Details of birth (vaginal delivery, vaginal delivery forceps/vacuum instrumental, cesarean – scheduled, cesarean – emergency)
- Gestational age (weeks)
- Sex (male, female)
- Weight (kg)
- Length (cm)
- Head circumference (cm)
- Apgar score 1 minute
- Apgar score 5 minute
- Apgar score 10 minute

Congenital anomalies

Characteristics at Screening

- Age (weeks)
- Sex (male, female)
- Weight-for-Age percentile categories
- Length/Height-for-Age percentile categories
- Head Circumference-for-Age percentile categories

Characteristics at Baseline

- Sex (male, female)
- Age (weeks)
- Exposure via breastmilk (months)

Medical History

Medical history of the infant will be summarized in the SAFI by System Organ Class (SOC) and preferred term (PT), following the same approach as previously described for medical history of the mother.

Vaccination Detail

Vaccination details of the infant will be listed in the SAFI.

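### For the non-MMR vaccines, SAP 4.5.5 and 4.5.6 pool titers from doses given before and after the mother's first postpartum infusion, which dilutes the evidence on response under exposure

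*SAP*

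**What the plan says.** - **Objective.** Protocol Section 2, Table 1 asks whether infants of treated women "are able to mount humoral immune responses to clinically relevant vaccines". The first endpoint is "Mean titers of antibody immune response(s) to common childhood vaccinations with full or partial doses given prior to 1 year". The second is the proportion with seroprotective titers.
- **Start of exposure.** Protocol 4.1.1 requires: "Infant is between 2–24 weeks of age at the time of the mother's first postpartum dose of ocrelizumab". Before that infusion the infant is meant to be unexposed, since SAP Section 2 admits women resuming ocrelizumab only if the "last exposure to ocrelizumab occurred more than 3 months before the LMP".
- **Doses that count.** Protocol 4.5.3.2: "Vaccines administered from birth throughout the end of the study should be recorded at Months 2, 4, 6, 9, and 12", and again at the last visit. SAP 4.5.5 takes "full or partial doses given prior to 1 year" and sets no starting point tied to the infusion.
- **Analysis.** The antibody analysis set (SAP 4.1.11) is every infant with any titer. SAP 4.5.6 gives the seroprotected proportion for each antibody: "Analysis will be presented by total as well as by women not switching to another DMT vs switching to another DMT regardless of timing". The one sensitivity analysis changes the tetanus and diphtheria threshold for infants who had a fourth dose. On infant vaccination data, SAP 4.3.2 says only: "Vaccination details of the infant will be listed in the SAFI".

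**The concern.** The question is about response under exposure, but the summary does not separate doses given under exposure from doses given before it. Part of an infant's titer at about Month 13 may come from priming that preceded any ocrelizumab in the milk. Such an infant counts in the pooled proportion exactly as one vaccinated entirely after the infusion.

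The planned split does not repair this. A mother may switch DMT after her infant's last dose and still be a switcher. An infant vaccinated before the infusion, or weaned early, may have a mother who never switches.

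If ocrelizumab in milk did weaken responses, doses given before exposure would soften that signal. For an infant-safety question this is the reassuring direction. The SAP applies exposure rules elsewhere: for the B-cell endpoint, SAP 4.4.1 excludes infants who had no breastmilk in the 30 days after the infusion, and infants whose mothers used another DMT. The vaccine endpoints have no comparable rule.

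**Working it through.** **1. The plan's own precision figures.** SAP 2.2 gives figures only for the B-cell endpoint. Exact Clopper-Pearson limits for n = 10:
- 1/10: 0.0025 to 0.4450, width 0.4425 (plan 0.443)
- 2/10: 0.0252 to 0.5561, width 0.5309 (plan 0.531)
- 0/10: upper limit 0.3085 (plan 0.31)

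These agree to within 0.001 for the widths and to rounding for the upper limit. No figure is stated for seroprotection, so this point contradicts no number in the plan.

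**2. Direction.** Let f be the share of infants whose titer rests on pre-infusion doses, p0 their seroprotection rate, and p1 the rate in infants vaccinated after the infusion. Then:

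pooled = f × p0 + (1 − f) × p1, so pooled − p1 = f × (p0 − p1).

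If exposure lowers response (p1 < p0), the pooled figure exceeds p1. A mixed series lies between the two extremes and dilutes less. The documents give none of f, p0 or p1.

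**3. How often doses could precede the infusion.** Protocol 4.5.3.2 leaves schedules to each country and gives no dose ages. Assume infusion age is uniform over 2 to 24 weeks. The share of infants who have already had a dose scheduled at week w is (24 − w)/22:

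| Dose at week | Given before infusion |
|---|---|
| 6 | 18/22 = 82% |
| 8 | 16/22 = 73% |
| 12 | 12/22 = 55% |
| 16 | 8/22 = 36% |
| 20 | 4/22 = 18% |

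A series is wholly pre-infusion only if its last dose is. Read for the last dose, the same column gives 55% if the series ends at week 12, 18% if it ends at week 20, and 0% if it ends at week 24 or later.

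**4. Mixed series, on one assumed schedule.** Take doses at 2, 4 and 6 months, that is weeks 8.7, 17.4 and 26.1 (months × 30.4375/7).
- All doses after the infusion: (8.7 − 2)/22 = 30%
- At least two doses before: (24 − 17.4)/22 = 30%
- Exactly one dose before: 100% − 30% − 30% = 40%
- All three before: 0%, because the latest infusion (24 × 7/30.4375 = 5.5 months) precedes the third dose

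So on this schedule about 70% of completed series would be mixed, and only an incomplete series could be wholly pre-infusion.

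**5. MMR.** Protocol 3.1.1 times the titer to 1 month (+30 days) after a first MMR dose given at 11 months or later, or after the second dose if the first came earlier. The infusion is at 24 weeks at the latest. The dose that triggers the titer therefore follows it.

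**6. Precision of a split.** When all n infants respond, the lower limit is 0.025^(1/n): 10/10 gives 0.69, 7/7 gives 0.59, 5/5 gives 0.48 and 3/3 gives 0.29.

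**The case against.** **The SAP does what the protocol asks.** Table 1 defines the endpoint on all doses before 1 year, Protocol 6.5.2 asks for the overall population, and no hypothesis is tested. This stands: the pooling is not an error in carrying out the protocol. It still leaves the summary short of the objective.

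**The plan already contains a post-infusion response test.** Measles, mumps and rubella are three of the nine tests in SAP 4.5.6. This stands and limits the point to the other vaccines.

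**With about 10 infants, listings may be enough.** Vaccination, titers and feeding are all listed, so a reader can look case by case. This stands in part. No planned output classifies a dose against the infusion date, and the proportions that will be quoted are pooled.

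**Stronger readings that the documents do not support.**
- A reader might infer that infants entering near 24 weeks are effectively unexposed at vaccination, and put a figure on the inflation. Step 4 shows that on a plausible schedule even the latest entrant has a dose after the infusion, and the documents supply no response rates.
- A reader might want to replace the DMT-switch split with exposure at each dose date, using the 182-day window. SAP 4.8.1 defines that window for the mother's treatment duration. Protocol 3.3 expects milk excretion to be highest in the first 60 days. After the sampling period, feeding status is recorded only at Months 2, 4, 6, 9 and 12. The SAP also never describes non-switchers as continuing on ocrelizumab, so the split is not mislabelled.
- A reader might rest the whole conclusion on series begun after the infusion. In step 4 that is about 3 of 10 infants, too few to carry it.

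**Conclusion.** The point holds for diphtheria, tetanus, pertussis, Hib, HBV and PCV-13. No analysis set, summary, subgroup or sensitivity analysis relates a vaccine dose to the mother's first postpartum infusion, and the DMT-switch split is not a substitute. The pooled proportion therefore mixes response under exposure with priming before it. If exposure impairs response, the pooled figure errs toward reassurance.

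The size cannot be computed from the documents. The percentages above rest on a uniform infusion age and assumed dose ages, and show only that pre-infusion doses could be common. For many infants the effect will be dilution by mixed series, not replacement by wholly unexposed ones. This is a cheap improvement to a descriptive endpoint. It does not show that the planned result would be wrong.

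**What to change.** In SAP 4.5.5 and 4.5.6, for each infant and each non-MMR vaccine:

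1. Use vaccination and infusion dates to classify the series as all doses before, mixed, or all doses after the first postpartum infusion.
2. Add this class to the titer and seroprotection listings.
3. Show titers and seroprotection by class as a descriptive split, beside the pooled total and the existing DMT-switch split, both of which stay.
4. Add a sensitivity summary limited to infants with at least one dose of that vaccine after the infusion. Wholly pre-infusion series then do not support a statement about response under exposure.

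**Cost.** One derived variable, one listing column and a table split, with no new procedures. Vaccines are recorded from birth, the first postpartum infusion date is used throughout the SAP, and the fourth-dose rule in SAP 4.5.6 already needs vaccine dates. The downside is small classes with wide intervals (step 6), so the split should be read as description only.
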